#### Secondary outcome analysis

#### GIH

Analyse the frequency score after treatment with the active product compared to baseline and contrast that to the score after the placebo treatment. To report what proportion and number of participants showed a reduction in the frequency score after active treatment, what the mean reduction was with confidence interval.

#### ABC

Analyse the ABC scores after treatment with the active product compared to baseline and contrast that to the scores after the placebo treatment. To report what proportion and number of participants that showed a reduction in the total score and the subscale scores for Irritability, Lethargy/social withdrawal, Stereotypic behaviour and Hyperactivity after active treatment, what the mean reduction was with confidence interval.

#### **APSI**

Analyse the APSI score after treatment with the active product compared to baseline and contrast that to the score after the placebo treatment. To report what proportion and number of participants that showed a reduction in the score after active treatment, what the mean reduction was with confidence interval.

#### Clinician's global assessment

Analyse the Clinician's global assessment after treatment with the active product compared to baseline and contrast that to the assessment after the placebo treatment. To report what proportion and number of participants that showed an improvement after active treatment.

#### Sensitivity and other planned analyses

Sensitivity analysis of data outliers will be presented by showing data as box-plots.

Non-adherence to the protocol will be handled by performing intention to treat and per protocol analyses as necessary.

Missing data will be handled by inputting the missing data and redoing the analysis.

Data will be analysed for normality, and those which are not normally distributed will be non-parametrically assessed.

A more detailed statistical analysis plan will be produced prior to the final analysis. The plan will be reviewed and possibly updated as a result of the blind review of the data and will be finalised before breaking the blind. Formal records should be kept of when the statistical analysis plan was finalised as well as when the blind was subsequently broken.

## **Qualitative Assessment of the Study experience - Phase 3**

The proposed randomised placebo controlled crossover trial, includes a theory-driven process evaluation. This will be informed by realist evaluation methodology [R. Pawson, N. Tilley, Realistic Evaluation. London: Sage; 2009], which goes beyond the evaluation question "What works?" to: "What works, for whom and in what context?" The aim of this approach is to situate and explain outcomes within the contexts in which they are achieved in order to explain potential discrepancies between expected and observed outcome and to assess fidelity to the treatment plan. Furthermore, the results of the process evaluation will provide data to inform the optimisation of the intervention. The objectives of the process evaluation are as follows:

- To explore the fidelity to the treatment plan (to be embedded within data collection on implementation contexts)
- To explore implementation contexts (including demographics, delivery of the treatment; adherence and non-completion),
- To explore intervention optimisation

Contextual data will be gathered on all participants via the clinical assessment form, GIH and dietary assessment, in order to explore pre-existing background contexts and any changes (e.g. change in diet, treatment with medication) that might have an impact on efficacy of the treatment. Data on the fidelity to treatment plan will be gathered via the semi-structured phone and clinic interviews with participants and also by recording the number of unused sachets brought back to the clinic by participants.

Qualitative data relevant to the optimisation of the intervention will be gathered during final interviews with the parents, either at completion of the study or on exiting the study

### **Interview study methods**

Interviews will be conducted with the parents of participants at six time points when we will collect Phase 3 qualitative data alongside primary and secondary outcome measures. In-person interviews will be conducted at the beginning of the study, at the crossover point and on completion of the study, or on exiting the study. Support phone calls in Week 5, 9, 21 and 25 or at drop-out, will be made by the researcher who will also include a short semi-structured interview with participants. During the support phone calls the researcher will collect qualitative data about how the parents are coping with administering the treatment and how the experience compares to their expectations. The interviews will not be recorded. The researcher will use a checklist for the interview and notes will be written on this checklist and this will be stored in the CRF.

Phase 3 will explore the acceptability of treatment, expectations of participants versus actual experience; barriers and facilitators to compliance; the quality of information provision; the parent's experience of implementation processes such as questionnaire completion. Particular attention will be paid to including the views of non-completing participants to explore reasons for non-adherence and their views on how the intervention experience might have been improved. The telephone interviews will last approximately 30 minutes. With the parent's consent, the interview will be recorded on a digital voice recorder and stored temporarily in a locked drawer until transcribed. Once it has been transcribed the voice recording will be deleted. The transcript will be identified by the participant number and no identifying details of the participant or parent will be recorded in the transcript.

# **Record keeping and archiving**

At the end of the trial, all essential documentation will be archived securely by the CI for a minimum of 20 years for the declaration of the end of the trial.

Essential documents are those which enable both the conduct of the trial and the quality of the data produced to be evaluated and show whether the site complied with all applicable regulatory requirements.

The sponsor will notify UCLH when trial documentation can be archived. All archived documents must continue to be available for inspection by appropriate authorities upon request.

## **Oversight Committees**

Trial Management Group (TMG)

Data Monitoring Committee (DMC)

Trial Steering Committee (TSC)

### **Trial Management Group**

The TMG will include the Chief Investigator and trial staff. The TMG will be responsible for overseeing the trial. The group will have regular meetings (approximately 3 times per year).

The TMG will review recruitment figures, SAEs and substantial amendments to the protocol prior to submission to the REC.

### **Other committees**

### **Trial Steering Committee**

The role of the TSC is to provide overall supervision of the trial. The TSC will review the recommendations of the Data Monitoring Committee and, on consideration of this information, recommend any appropriate amendments/actions for the trial as necessary. The TSC acts on behalf of the funders and Sponsor.

The Trial Steering Committee will meet/phone the Chief Investigator and Principal Investigator on a fixed monthly basis to confirm the procedures are being followed. They will have access to randomly inspect this process according to their discretion. This Committee will include a patient parent representative.

#### **Data Monitoring Committee**

The role of the DMC is to provide advice on data and safety aspects of the trial but where not all members are independent. Meetings of the Committee will be held at 6 monthly intervals to review interim analyses, or as necessary to address any issues.

It is anticipated that the members will meet once to agree the terms of reference and on at least two further occasions to monitor accumulating data and oversee safety issues. During the period of recruitment to the trial, interim analyses will be supplied, in strict confidence, to the DMC, together with

any other analyses that the committee may request. This may include analyses of data from other comparable trials. In the light of these interim analyses, the DMC will advise the Trial Steering Committee if, in its view Vivomixx has been proved, beyond reasonable doubt, to be different from the control (placebo) for all or some types of patients (in respect of either effectiveness or unacceptable safety concerns).

The Trial Steering Committee can then decide whether or not to modify intake to the trial. Unless this happens, however, the Trial Management Group, clinical collaborators and trial office staff (except those who supply the confidential analyses) will remain blinded of the interim results. The frequency of interim analyses will depend on the judgement of the DMC. However, we anticipate

that there will be one interim analysis and one final analysis.

## Ethical requirements and participant and public involvement Ethics

The sponsor will ensure that the trial protocol, participant information sheet, consent form, GP letter and submitted supporting documents have been approved by the appropriate research ethics committee, prior to any participant recruitment. The protocol, all other supporting documents including and agreed amendments, will be documented and submitted for ethical and regulatory approval as required. Amendments will not be implemented prior to receipt of the required approval(s).

Before any NHS site may be opened to recruit participants, the Chief Investigator/Principal Investigator must receive NHS permission in writing from the Trust Research & Development (R&D). It is the responsibility of the CI/ PI to ensure that all subsequent amendments gain the necessary approvals, including NHS Permission (where required) at the site. This does not affect the individual clinician's responsibility to take immediate action if thought necessary to protect the health and interest of individual participants (see earlier section on Reporting Urgent Safety Measures).

An annual progress report (APR) will be submitted to the REC within 30 days of the anniversary date on which the favourable opinion was given, and annually until the trial is declared ended. The chief investigator will prepare the APR.

Within 90 days after the end of the trial, the CI/Sponsor will ensure that the main REC is notified that the trial has finished. If the trial is terminated prematurely, those reports will be made within 15 days after the end of the trial.

The CI will supply the Sponsor with a summary report of the trial, which will then be submitted to the REC within 1 year after the end of the trial.

### Patient and public involvement (PPI)

Patients and the public have been involved in the design of the research. We used the results of our survey of parents of children with ASDs to inform our choice of outcome measures. We consulted with parents of children with ASDs about the acceptability of a 4-week washout period and we sought the

ASD - vivomixx protocol v6 .docx, IRAS 204582, Version 6.0, 30/01/2020, Page 47 of 57

views of children with ASDs on our Child Information Sheet. The study protocol has been reviewed by parents' of children with ASDs and also by the London Autism Research Advisory Group (https://m.facebook.com/laragresearch).

Patients and the public will be involved in the management of the research and analysis of results as the Trial Steering Committee will include a Patient Participation representative and a member of London Autism Research Advisory Group.

The dissemination of the findings to parents of children with ASDs will be via parent-led and parent-focused charities.

## Monitoring

The sponsor will determine the appropriate level and nature of monitoring required for the trial. Risk will be assessed on an ongoing basis and adjustments made accordingly.

The degree of monitoring will be proportionate to the risks associated with the trial.

A trial specific oversight and monitoring plan will be established for studies. The trial will be monitored in accordance with the agreed plan.

## Finance

This trial is supported by,

- 1. Principal Investigator's salary from Caudwell Children
- 2. Provision of product and placebo by company grant
- 3. Administration support from Caudwell Children

The CI, PI and TMG members hold no financial interests in Vivomixx or Gastropharm.

## Insurance

University College London holds insurance against claims from participants for injury caused by their participation in the trial. Participants may be able to claim compensation if they can prove that UCL has been negligent. However, as this trial is being carried out in a hospital, the hospital continues to have a duty of care to the participant of the trial. University College London does not accept liability for any breach in the hospital's duty of care, or any negligence on the part of hospital employees. This applies whether the hospital is an NHS Trust or otherwise.

Participants may also be able to claim compensation for injury caused by participation in this trial without the need to prove negligence on the part of University College London or another party. Participants who sustain injury and wish to make a claim for compensation should do so in writing in the first instance to the Chief Investigator, who will pass the claim to the Sponsor's Insurers, via the Sponsor's office.

Hospitals selected to participate in this trial shall provide negligence insurance cover for harm caused by their employees and a copy of the relevant insurance policy or summary shall be provided to University College London, upon request.

## **Publication policy**

The success of the trial depends entirely on the wholehearted collaboration of a large number of participants with ASD and their parents or carers. A trial publication policy will be developed. The results of the trial will be reported first to study collaborators. The main report will be drafted by the Trial Management Group and circulated to all collaborators for comment. The final version will be agreed by the Data Monitoring Committee and Trial Steering Committee before submission for publication, on behalf of all the trial collaborators.

All proposed publications will be discussed with and reviewed by the Sponsor prior to publishing other than those presented at scientific forums/meetings. Please refer to UCL publication policy.

# Appendices

Appendix 1 Schedule of Assessments and Procedures

- PP	Ta: eva	aluation	12 week randomised treatment					Wa	shout		12 week crossover treatment										Exit Interview										
Placebo	Da	y 1-7																													
Placebo or Probiotic				•				Day	8 - 7	76																					
No Treatment															Day	77-10	)4														
Placebo or Probiotic																			Day 105 - 189												
Final Assessment																															Day 190 - 196
WEEK	1		2	3	4	5	6	7	8	9	10	11	12	13	14	15	16	17	18	19	20	21	22	23	24	25	26	27	28	29	30
Medical History	Р																														
GI History	R														R																R
Diet assessment	R																														
ATEC	P	0													P O																PO
ABC	Р	0													P O																ΡΟ
APSI	Ρ														P																P
Global assessment	R														R																R
Phone interview						P R				P R												P R				P R					
Clinic visit	P	R	P R												P R																PR
Collect stool sample	P														P																P

**KEY P** = Parent/guardian

**O** = Educator

**R** = Researcher

Q

caudwell children Changing Children's Lives

#### Schedule of Treatment

	Treatment	Treatment product	Dose for 3 – 10	Dose for 11 – 16			
	stage		year old	year old			
Week 1	Taste	Placebo	1 sachet daily for	1 sachet daily for			
	evaluation		, 3 days	3 days			
Week 2	Part 1	Randomised Vivomixx	1 sachet daily	1 sachet twice			
		or placebo	,	daily			
Week 3	Part 1	Randomised Vivomixx	1 sachet daily	1 sachet twice			
		or placebo		daily			
Week 4	Part 1	Randomised Vivomixx	1 sachet daily	1 sachet twice			
		or placebo		daily			
Week 5	Part 1	Randomised Vivomixx	1 sachet daily	1 sachet twice daily			
		or placebo					
Week 6	Part 1	Randomised Vivomixx	1 sachet twice	3 sachets daily			
		or placebo	daily	split over 2 or 3			
				doses			
Week 7	Part 1	Randomised Vivomixx	1 sachet twice	3 sachets daily			
		or placebo	daily	split over 2 or 3			
				doses			
Week 8	Part 1	Randomised Vivomixx	1 sachet twice	3 sachets daily			
		or placebo	daily	split over 2 or 3			
				doses			
Week 9	Part 1	Randomised Vivomixx	1 sachet twice	3 sachets daily			
		or placebo	daily	split over 2 or 3			
				doses			
Week 10	Part 1	Randomised Vivomixx	1 sachet twice	3 sachets daily			
		or placebo	daily	split over 2 or 3			
				doses			
Week 11	Part 1	Randomised Vivomixx	1 sachet twice	3 sachets daily			
		or placebo	daily	split over 2 or 3			
				doses			
Week 12	Part 1	Randomised Vivomixx	1 sachet twice	3 sachets daily			
		or placebo	daily	split over 2 or 3			
M. 1.60			4	doses			
Week 13	Part 1	Randomised Vivomixx	1 sachet twice	3 sachets daily			
		or placebo	daily	split over 2 or 3			
Mack 14	Machaut	No troatment		doses			
Week 14 Week 15	Washout Washout	No treatment					
Week 15 Week 16	Washout	No treatment No treatment					
Week 10 Week 17	Washout	No treatment					
End of	Crossover						
Week 17							
Week 18	Part 2	Randomised Vivomixx	1 sachet daily	1 sachet twice			
Mark 10	Davit 2	or placebo	4	daily			
Week 19	Part 2	Randomised Vivomixx	1 sachet daily	1 sachet twice			
		or placebo		daily			

Week 20	Part 2	Randomised Vivomixx	1 sachet daily	1 sachet twice
		or placebo		daily
Week 21	Part 2	Randomised Vivomixx	1 sachet daily	1 sachet twice
		or placebo		daily
Week 22	Part 2	Randomised Vivomixx	1 sachet twice	3 sachets daily
		or placebo	daily	split over 2 or 3
				doses
Week 23	Part 2	Randomised Vivomixx	1 sachet twice	3 sachets daily
		or placebo	daily	split over 2 or 3
				doses
Week 24	Part 2	Randomised Vivomixx	1 sachet twice	3 sachets daily
		or placebo	daily	split over 2 or 3
				doses
Week 25	Part 2	Randomised Vivomixx	1 sachet twice	3 sachets daily
		or placebo	daily	split over 2 or 3
				doses
Week 26	Part 2	Randomised Vivomixx	1 sachet twice	3 sachets daily
		or placebo	daily	split over 2 or 3
				doses
Week 27	Part 2	Randomised Vivomixx	1 sachet twice	3 sachets daily
		or placebo	daily	split over 2 or 3
				doses
Week 28	Part 2	Randomised Vivomixx	1 sachet twice	3 sachets daily
		or placebo	daily	split over 2 or 3
				doses
Week 29	Part 2	Randomised Vivomixx	1 sachet twice	3 sachets daily
		or placebo	daily	split over 2 or 3
				doses
Week 30	Exit			
	interview

The efficacy of the multi-strain probiotic, Vivomixx, on behaviour and gastrointestinal symptoms in children with autism spectrum disorder (ASD)

NCT03369431

18th March 2021

Statistical Analysis Plan

Principal Analysis

The principal analysis will look for between phase differences in outcome measures assuming no order of treatment effects, which will be investigated in the secondary analysis. The outcome variables consider are:

1. Change from baseline ATEC scores (**Interval Data: between groups**): **PRIMARY OUTCOME MEASURE**

Secondary measures

1. Change from baseline ABC scores (**Interval Data: between groups**)
2. Gastrointestinal events: frequency of abdominal pain, gaseousness, diarrhoea, constipation, pain on stooling, and difficulty swallowing. (**Interval Data: between groups**)
3. Bristol Stool Scale: proportion of phase participants with type 4 stool samples after active treatment. (**Dichotomous data: between groups**)
4. Clinical Global Impression (**Interval Data: between groups**)
5. Treatment Effectiveness Score (**Interval Data: between groups**)
6. Correlations: ATEC vs constipation frequency on GI History; ATEC vs diarrhoea frequency on GI History; ATEC vs ATEC components (i.e. Health/Physical/Behaviour scores); ATEC vs Clinical Global Impression. (**Interval Data: Correlation**)

All between groups interval data will be subject to the following protocol for statistical analysis.

1. Calculation of mean, standard error and median and 25-75 quartiles for both phases.
2. Kolmogorov-Smirnov test to assess normality in the between phase differences in primary and secondary outcome measure with interval measurements.
3. If there is no statistically significant ($\alpha = 0.05$) evidence of non-normality in the mean differences then a paired t-test¹ will be used to assess statistical significance.
4. If there is statistically significant ($\alpha = 0.05$) evidence of non-normality in the mean differences, then a Wilcoxon-Signed-rank-test will be used to assess statistical significance.

All between groups dichotomous data will be assessed for statistical significance by calculating the Relative Risk and corresponding 95% confidence intervals for exposure to the active agent. Corresponding p-values can, if desired, be calculated from the 95% Confidence Intervals; however, 95% Confidence Intervals that do not contain the value 1 are statistically significant at $\alpha = 0.05$.

The correlations will be measured using Pearson's R unless the assumptions for Pearson's R are not met: if these are not met, then Spearman's Rho will be used. The relevant assumptions for Pearson's R are:

1. Absence of outliers: i.e. no outliers for each variable more than ± 3.29 Standard deviations from the mean.
2. Normality of variables: both variables will be assessed for normality using a Kolmogorov-Smirnov test.
3. Linearity: the relationship follows a straight-line relationship

¹ Note: assumption for paired-t-test is that the differences between the pairs are values are normally distributed, not that the values in each phase need to be normally distributed. The test does not assume homoscedasticity: i.e. that the standard deviations of the two groups are the same, so we will not test for this.

4. **Homoscedasticity:** how the datapoints are similarly distributed about a straight-line linear regression does not vary as either variables varies (technically the Standard error does not change significantly).

Assumptions three and four can be assessed visually using a scatter plot with a linear regression line added, and this can be generated by SPSS.

Secondary Analysis

Safety Analysis

The number of adverse events will be recorded that occurred to participants whilst on the active agent and placebo phases. The results will be presented both descriptively and assessed for a statistical difference in risk. To do this, the Relative Risk (RR) of adverse event as due to exposure to the active agent will be calculated with corresponding 95% confidence intervals.

Adherence and Deviation from Protocol Analysis

Similarly, adherence will be analysed descriptively for both the placebo and active agent phases, with totals for longer washout, withdrawal, lost to follow-up, did not reach full dose recorded for each phase. The total number of deviations will be summed for each phase, and the Relative Risk (RR) of deviation due to exposure to the active agent calculated with corresponding 95% confidence intervals.

Order of Treatment Effects

This analysis will replicate the between groups principal analysis; however, it will compare outcomes between the placebo/active and the active/placebo groups of participants rather than between the placebo arm and the active agent arm. Where dichotomous between groups data is considered, the Risk of exposure to the active agent in the first phase will be calculated with 95% confidence intervals.

The principal analysis of the primary outcome measure will be performed on the Placebo-first group vs Placebo-second group, and between the Active-first group vs the Active-second group to assess for an order effect.

Order of Treatment group demographics

The demographics of the placebo/active and the active/placebo groups of participants, will be analysed and compared for significant differences. The characteristics that will be analysed are age, gender, baseline ATEC total score and additional diagnoses.

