# **Protocol Summary**

Questions addressed: Type of trial:	Is Vivomixx an effective agent in ASD children who also have GI symptoms in terms of improving overall functional level and is this associated with a reduced frequency of gastrointestinal symptoms? Does this intervention improve the quality of life of the patient and their parents? A single-site randomised double blind placebo controlled crossover trial in children with autistic spectrum disorder and gastrointestinal symptoms.
Trial duration per participant:	30 weeks
Estimated total trial duration:	1 year
Interventions:	
 
Daily administration of Vivomixx probiotic powder mixed into a drink or selected cold foods
 
Daily administration of placebo powder mixed into a drink or
 

Outcome assessment:	
 
selected cold foods
 
Parent completed questionnaires after 12 weeks of treatment and after 28 weeks of treatment
 
Educator completed questionnaires after 12 weeks of treatment and after 28 weeks of treatment
 
Clinician completed assessments after 12 weeks of treatment and after 28 weeks of treatment
 

Planned trial sites: Total number of participants planned:	Single-site 82
Main inclusion/exclusion criteria:	
 
Children aged between 3 – 16 years of age, with a diagnosis of ASD and gastrointestinal symptoms excluding those,
 
with Retts Syndrome and Fragile X
 
on NSAIDs
 
taken antibiotics in the past month
 
taken a probiotic in the past month
 
history of intolerance or allergy to probiotics
 

Statistical methodology and analysis	The intention-to-treat (ITT) analysis will be performed on all patients who are randomised. An additional analysis will be done on only those patients who complete the study per protocol analysis. Changes in ASD scores during follow-up will be examined using the mixed model for analysis of variance to account for missing data (dropouts). The mixed model will use group (treatment versus control) and time as factors. If residuals prove not to be normally distributed the Bonferroni multiple comparisons with Bootstrap multiple comparisons to accommodate for the non-normality of residuals will be done. A P -value < 0.05 is considered significant and multiple comparisons
ASD - vivomixx protocol v6 .d	locx, IRAS 204582, Version 6.0, 30/01/2020, Page 8 of 57

will be undertaken with Fisher's least significant difference test and 95% confidence intervals.

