## Sample size calculation

#### Sample size calculation

To determine an effect size of 0.50 with 80% power, a sample size of 72 with a type 1 error of 5% using a two-sided test would be sufficient. Assuming a 15% drop out rate, 82 patients will be enrolled. The sample size calculation is based on the assumed effect size of the primary outcome measure, the Autism Treatment Evaluation Checklist (ATEC), which is a ASD composite function score). The minimally clinically important difference based on the primary outcome measure with this instrument was 15 points. Given previous probiotic efficacy data, the effect size of 15 points is a reasonable assumption. Previous studies have shown that assuming ATEC data to be normally distributed is reasonable. Assuming a dropout rate of 10%, our sample size is reduced from 82 to 74. With a type 1 error rate of 5%, and required power of 80%, a non-parametric matched pairs analysis (Wilcoxon Signed-Rank Test) with an assumed low correlation between the subjects in the two conditions (rho=0.2), G\*Power 3.1.7 calculated that the study would achieve and 80% with a Cohen's dz effect size of 0.34. This equates to a small to medium Cohen's standard effect size of 0.37, as adjusted using the correction given in Myers, Well, & Lorch (2010) on page 147 equation 6.28.

[Myers, J.,, Well, A., and Lorch, R., 2010. *Research design and statistical analysis*. [online] Available at: <https://books.google.co.uk/books?hl=en&lr=&id=nbsOIJ\_saUAC&oi=fnd&pg=PR2&dq=Research+Design+and+Statistical+Analysis:+Third+Edition&ots=ZwDnkDkrpH&sig=IVDU30D2I5sa5MMmvqAOw5FstZc> [Accessed 10 May 2017].]

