#### Primary outcome analysis

The intention-to-treat (ITT) analysis will be performed on all participants who are randomised. An additional analysis will be done on only those participants who complete the study per protocol analysis.

Change in the ATEC score during follow-up will be examined using the mixed model for analysis of variance to account for missing data (dropouts). This model allows the evaluation of the effect of each factor on the outcome as well as the interactions between factors. The mixed model will use group (treatment ASD - vivomixx protocol v6.docx, IRAS 204582, Version 6.0, 30/01/2020, Page 43 of 57

versus control) and time as factors. If residuals prove not to be normally distributed, the Bonferroni multiple comparisons with Bootstrap multiple comparisons to accommodate for the non-normality of residuals will be done. A P-value <0.05 is considered significant and multiple comparisons will be undertaken with Fisher's least significant difference test and 95% confidence intervals.

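### The SAP's primary ATEC test uses only children with both phase scores, conflicts with the protocol's ITT mixed model, and names no analysis set, missing-data rule or confidence interval for the difference

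*SAP*

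**What the plan says.** **Protocol, Primary outcome analysis** (repeated in the Protocol Summary). "The intention-to-treat (ITT) analysis will be performed on all participants who are randomised", with a further per-protocol analysis. "Change in the ATEC score during follow-up will be examined using the mixed model for analysis of variance to account for missing data (dropouts"). On its terms: "The mixed model will use group (treatment versus control) and time as factors". Intervals appear in the sentence on follow-on tests: "multiple comparisons will be undertaken with Fisher's least significant difference test and 95% confidence intervals".

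**Protocol, Sensitivity and other planned analyses.** "Missing data will be handled by inputting the missing data and redoing the analysis". The same section sends non-normal data to non-parametric methods. It also foresees a more detailed SAP, to be final before unblinding, with formal records of both dates.

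**Protocol, Sample size calculation.** The calculation that names a test uses "a non-parametric matched pairs analysis (Wilcoxon Signed-Rank Test) with an assumed low correlation between the subjects in the two conditions (rho=0.2"), with 82 children reduced to 74, and states a minimally important ATEC difference of 15 points.

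**SAP, Principal Analysis.** "The principal analysis will look for between phase differences in outcome measures assuming no order of treatment effects". Each phase is summarised by mean, standard error, median and quartiles. A Kolmogorov-Smirnov test on the phase differences then selects a paired t-test or, if normality is rejected, "a Wilcoxon-Signed-rank-test will be used to assess statistical significance". Confidence intervals are specified only for relative risks.

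**SAP, Secondary Analysis.** Withdrawals and losses to follow-up are counted per phase as deviations. Order is checked by comparing placebo-first with placebo-second children, and active-first with active-second children.

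**The concern.** A paired test uses only children who have both scores, whereas the protocol's primary analysis covers all randomised children and picks its model because some will drop out. The SAP expects withdrawals, since it tabulates them, but gives no rule for how those children enter the ATEC test. From the two documents a reader cannot tell who is in the primary comparison or whether the protocol's imputation still applies.

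Three things are at stake. Children with a Visit 3 score but no Visit 4 score contribute nothing. A general shift between periods adds noise to the paired differences, and adds bias if the two sequences end with unequal numbers of pairs. And the result would come as a p-value with phase-wise summaries. The standard errors of the two phases do not yield the interval for a paired difference, so nothing planned can be set against the 15-point threshold.

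**Working it through.** **1. The protocol's own power figure.** Wilcoxon signed-rank, 74 pairs, dz 0.34, two-sided 5%. With asymptotic relative efficiency 3/π (normal data), effective n = 74 × 0.955 = 70.7 and noncentrality = 0.34 × √70.7 = 2.86. Power is 80.5%, against 80% stated, so it reproduces.

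**2. Children without a pair.** 82 × 0.10 = 8.2 and 82 × 0.15 = 12.3, leaving about 74 or 70 pairs. Paired t-test power at dz 0.34 is 0.86 with 82 pairs, 0.82 with 74 and 0.80 with 70.

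**3. Assumed inputs.** The protocol gives no ATEC SD and does not connect 15 points, effect size 0.50 and dz 0.34. Two SDs were used: 15/0.34/√(2 × 0.8) = 34.9, and 15/0.50 = 30. Correlation was 0.2 (protocol) or 0.6 (assumed). Period shifts of 0, 5 and 10 points are assumptions. There is one baseline, so it cancels in a complete pair, and testing changes is the same as testing scores.

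**4. Power for a 15-point effect.** Simulated with 41 children per sequence and 15% random dropout after Visit 3; paired t-test v mixed model (treatment, period, sequence):

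| SD, rho | Shift 0 | Shift 5 | Shift 10 |
|---|---|---|---|
| 34.9, 0.2 | 0.80 v 0.82 | 0.80 v 0.82 | 0.79 v 0.83 |
| 30, 0.2 | 0.91 v 0.92 | 0.89 v 0.91 | 0.90 v 0.93 |
| 34.9, 0.6 | 0.98 v 0.98 | 0.98 v 0.98 | 0.97 v 0.98 |

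If dropout instead depends on the first-period score (SD 34.9, rho 0.2), power is 0.76 to 0.78 v 0.81 to 0.82.

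**5. Bias.** Under score-dependent dropout the paired estimate of a true 15 points is off by up to about 1 point, the model's by about 0.2 at most. Separately, unequal pairs bias the paired estimate by (n1 − n2)/(n1 + n2) × shift:
- 33 v 37: 4/70 × 5 = 0.3 and 4/70 × 10 = 0.6 points. With 12 random dropouts, a gap of 4 or more pairs has probability 0.35.
- 30 v 40: 10/70 × 5 = 0.7 and 10/70 × 10 = 1.4 points. A gap of 10 or more has probability 0.003.

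Type I error stays at 0.04 to 0.06 at these splits for shifts up to 10.

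**6. Noise from an ignored period shift.** With SD 30, rho 0.2 and 37 v 37 pairs, the SD of the difference is 30 × √1.6 = 37.9. The standard error is 37.9/√74 = 4.41 with period in the model, and √(37.9² + 10²)/√74 = 4.56 if a 10-point shift is ignored.

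**7. The interval the SAP omits.** With 74 pairs and rho 0.2, the 95% half-width is about 8.8 points at SD 30, and 11.9 at SD 40.5 (15/0.37, from the protocol's converted effect size). That is wide enough to matter when reading a result against 15 points.

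**8. The order checks.** They compare different children, so they are unpaired, although the SAP says they replicate the principal analysis. One check has power 0.09 to 0.11 for a 5-point shift and 0.23 to 0.31 for 10. At least one of the two is significant in 0.18 to 0.21 and 0.43 to 0.57 of trials, with a false-positive rate of about 0.09. The model's period term reaches 0.17 to 0.35 and 0.49 to 0.88 at a false-positive rate of 0.05.

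**The case against.** The SAP did not invent the paired test. The sample-size section uses a matched-pairs Wilcoxon, and the protocol sends non-normal data to non-parametric methods and allows a later, more detailed SAP. The conflict is therefore first inside the protocol, between its sample-size and primary-analysis sections. This stands. It explains the choice of test, but not who enters it.

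It can also be said that silence leaves the protocol's ITT set and imputation in force. A reader might infer that the SAP abandons both; the documents do not support that, because the SAP mentions neither. But if both still apply, the paired test needs a stated rule for children with one score, and none is given.

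A reader might infer that the SAP removed a period term and a planned interval for the primary contrast. The protocol names time, not period, and ties its intervals to multiple comparisons. The SAP states its no-order-effect assumption openly and checks it. So the period term is an improvement, not a restoration.

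The number without a pair may also be smaller than the dropout rate suggests. The protocol makes completion of the first treatment period a condition for second-period treatment, not for assessment, and it plans reminders and telephone completion.

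Finally, the gain is small, and the simulation covers only the t-test branch on normal data, without a baseline term. This stands too, and it limits how strongly the model can be urged.

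**Conclusion.** The concern holds as an unresolved conflict over the primary analysis, with a better method available at almost no cost. The protocol prescribes ITT with a mixed model; the SAP prescribes a test that, as written, is a complete-pairs analysis without period adjustment, and it does not state the analysis set, missing-data step or interval. It should be fixed.

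The size is modest: about 0.00 to 0.05 of power, up to about 1 point of bias on a true 15 when dropout depends on the first-period score, and 1.4 points in a rare 30 v 40 split with a 10-point shift. All of this rests on assumed SDs, correlations, shifts and dropout patterns.

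Two stronger readings fail. The paired test is not invalid: type I error is little affected, and under random dropout the expected bias from unequal pairs is zero. Nor does a mixed model repair everything. At SD 34.9, rho 0.2 and no shift, power is 0.86 with all pairs, 0.80 for the paired test after 15% dropout and 0.82 for the model, so it recovers (0.82 − 0.80)/(0.86 − 0.80), about a third of the loss. It removes bias only when dropout depends on observed scores; dropout that depends on unseen second-period scores was not examined.

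**What to change.** **Preferred.** Make the primary analysis a linear mixed model of change from baseline in ATEC at Visits 3 and 4, with treatment, period, sequence and baseline ATEC as fixed effects and participant as a random effect. Include every randomised child with at least one post-baseline ATEC. Report the active-placebo difference with its 95% CI beside the 15-point minimally important difference. Baseline belongs in the model because the outcome is a change score, and it does not cancel for children with one visit.

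Keep the paired t-test or Wilcoxon as a sensitivity analysis in complete pairs. Keep the protocol's imputation as a second one, so that children with no post-baseline score are covered. State that the placebo-first v placebo-second and active-first v active-second checks are unpaired, have low power and do not alter the primary estimate.

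**Minimum, if the paired test stays primary.** Name its analysis set, say how the protocol's ITT and imputation provisions apply, and add the 95% CI for the difference.

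**In either case.** Reconcile the protocol's sample-size, primary-analysis and sensitivity sections with the SAP, and give the reason for the departure. The SAP is dated 18 March 2021, but the documents do not say when the blind was broken. The change should be made before that point, or otherwise be reported as made after it.

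**Cost.** SAP wording and a few lines of code; no new data.
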